10.2 STATEMENT OF CONFIDENTIALITY

Individual patient medical information obtained as a result of this study is considered confidential and disclosure to third parties is prohibited with the exceptions noted below. Patient confidentiality will be ensured by using patient identification code numbers.

Treatment data may be given to the patient's personal physician or to other appropriate medical personnel responsible for the patient's welfare. Data generated as a result of the study need to be available for inspection on request by the participating physicians, the sponsor's representatives, by the IRB / IEC and the regulatory authorities <for EU>, *i.e. the CA*.

11. MANAGEMENT AND REPORTING OF ADVERSE EVENTS/ADVERSE REACTIONS

11.1 DEFINITION OF ADVERSE EVENTS

Adverse event

An adverse event (AE) is defined as any untoward medical occurrence in a patient or clinical investigation subject administered a medicinal product and which does not necessarily have a causal relationship with this treatment. An adverse event can therefore be any unfavorable and unintended sign (e.g. an abnormal laboratory finding), symptom, or disease temporally associated with the use of a medicinal product, whether or not considered related to the medicinal product.

Adverse reaction

An adverse reaction is defined as a response to a medicinal product which is noxious and unintended. Response in this context means that a causal relationship between a medicinal product and an adverse event is at least a reasonable possibility. Adverse reactions may arise from use of the product within or outside the terms of the marketing authorization or from occupational exposure. Conditions of use outside the marketing authorization include off-label use, overdose, misuse, abuse and medication errors.

Serious adverse event

A serious adverse event is defined as any AE which

- results in death,
- is life-threatening,
- requires in-patient hospitalization, or
- prolongation of existing hospitalization,
- results in persistent or significant disability or incapacity, or
- is a congenital anomaly/birth defect

Life-threatening in this context refers to a reaction in which the patient was at risk of death at the time of the reaction; it does not refer to a reaction that hypothetically might have caused death if more severe.

Medical and scientific judgment should be exercised in deciding whether other situations should be considered serious reactions, such as important medical events that might not be immediately life threatening or result in death or hospitalisation but might jeopardize the patient or might require intervention to prevent one of the other outcomes listed above.

Examples of such events are intensive treatment in an emergency room or at home for allergic bronchospasm, blood dyscrasias or convulsions that do not result in hospitalisation or development of dependency or abuse. Any suspected transmission via a medicinal product of an infectious agent is also considered a serious adverse reaction.

Table 1: Clinical criteria for Adverse Event of Special Interest

Endpoint	Definition
Acute liver injury	Any the following criteria: An elevation of AST and/or ALT \geq 3-fold ULN combined with an elevation of bilirubin \geq 2-fold ULN measured in the same blood draw sample. An isolated elevation of AST and /or ALT \geq 5-fold ULN irrespective of any bilirubin elevation
Decreased renal function	Creatinine value shows a \geq 2-fold increase from baseline and is above the upper limit of normal (ULN)
ketoacidosis and diabetic ketoacidosis (DKA)	Defined as a serious condition because of inability of body cells to get glucose as a source of energy, and subsequently, the body produces ketones as the result of burning fat for energy. DKA occurs because of a lack of insulin in the body, not enough food intakes in diabetic patients and insulin reaction (low blood glucose). It is characterized by high ketones levels, positive ketones in the urine and high pH levels. Specifically, for the SGLT2i induced DKA the blood glucose level may not be increased above 240 mg/dl.
Events involving lower limb amputation	This definition includes amputation (i.e. resection of a limb through a bone), disarticulation (i.e. resection of a limb through a joint) and auto-amputations (i.e. spontaneous separation of non-viable portion of the lower limb). Not included in this definition are debridement (removal of callus or dead tissue), procedures on a stump (like stump revision, drainage of an abscess, wound revision etc.) and other procedures (e.g., nail resection or removal) without a concomitant resection of a limb (amputation or disarticulation).” Request to report each lower limb amputation as separate AE

ALT = alanine aminotransferase; ULN = upper limit of normal range.

11.2 ADVERSE EVENT AND SERIOUS ADVERSE EVENT COLLECTION AND REPORTING

The investigator shall maintain and keep detailed records of all AEs in their patient files.

Collection of AEs

The study design is of non-interventional nature and the study is conducted within the conditions of the approved marketing authorization.

The following must be collected by the investigator in the e-CRF from signing the informed consent onwards until the end of the study:

- All adverse events

All AEs, including those persisting after study completion must be followed up until they are resolved, have been sufficiently characterized, or no further information can be obtained.

The investigator carefully assesses whether an AE constitutes an ADR using the information below.

AEs considered “Always Serious”

In accordance with the European Medicines Agency initiative on Important Medical Events, BI has set up a list of AEs, which by their nature, can always be considered to be “serious” even though they may not have met the criteria of an SAE as given above.

The latest list of “Always Serious AEs” can be found in the ISF. These events should always be reported in the eCRF as SAEs as described above.

Note: Cancers of new histology and exacerbations of existing cancer must be reported as a serious event regardless of the duration between discontinuation of the drug and the occurrence of the cancer.

Causal relationship of adverse event

The definition of an adverse reaction implies at least a reasonable possibility of a causal relationship between a suspected medicinal product and an adverse event. An adverse reaction, in contrast to an adverse event, is characterized by the fact that a causal relationship between a medicinal product and an occurrence is suspected.

Medical judgment should be used to determine the relationship, considering all relevant factors, including pattern of reaction, temporal relationship, de-challenge or re-challenge, confounding factors such as concomitant medication, concomitant diseases and relevant history.

Arguments that may suggest a **reasonable causal relationship** could be:

- The event is **consistent with the known pharmacology** of the drug
- The event is known to be caused by or **attributed to the drug class**.

- A **plausible time to onset of the event** relative to the time of drug exposure.
- Evidence that the **event is reproducible** when the drug is re-introduced
- **No medically sound alternative etiologies** that could explain the event (e.g. preexisting or concomitant diseases, or co-medications).
- The event is typically **drug-related and infrequent in the general population** not exposed to drugs (e.g. Stevens-Johnson syndrome).
- An indication of dose-response (i.e. greater effect size if the dose is increased, smaller effect size if dose is diminished).

Arguments that may suggest that there is **no reasonable possibility of a causal relationship** could be:

- No plausible time to onset of the event relative to the time of drug exposure is evident (e.g. pre-treatment cases, diagnosis of cancer or chronic disease within days/weeks of drug administration; an allergic reaction weeks after discontinuation of the drug concerned)
- Continuation of the event despite the withdrawal of the medication, taking into account the pharmacological properties of the compound (e.g. after 5 half-lives). Of note, this criterion may not be applicable to events whose time course is prolonged despite removing the original trigger.
- Additional arguments amongst those stated before, like alternative explanation (e.g. situations where other drugs or underlying diseases appear to provide a more likely explanation for the observed event than the drug concerned).
- Disappearance of the event even though the study drug treatment continues or remains unchanged.

Intensity of adverse event

The intensity of the AE should be judged based on the following:

Mild:	Awareness of sign(s) or symptom(s) which is/are easily tolerated
Moderate:	Enough discomfort to cause interference with usual activity
Severe:	Incapacitating or causing inability to work or to perform usual activities

Pregnancy:

In rare cases, pregnancy might occur in a study. Once a subject has been enrolled into the study, after having taken Jardiance, the investigator must report any drug exposure during pregnancy, which occurred in a female subject or in a partner to a male subject to the Sponsor by means of Part A of the Pregnancy Monitoring Form. The outcome of the pregnancy associated with the drug exposure during pregnancy must be followed up and reported by means of Part B of the Pregnancy Monitoring Form.

In the absence of a reportable AE, only the Pregnancy Monitoring Form must be completed, otherwise the NIS AE form is to be completed and forwarded as well within the respective timelines.

Table 2: Expedited Reporting of AEs and Drug Exposure During Pregnancy

The following must be reported by the investigator on the NIS AE form from signing the informed consent onwards until the end of the study:

Type of Report	Timeline
All Serious Related Adverse Events (SAEs) with Jardiance® , Trajenta® and/or Synjardy®	immediately within 24 hours
Adverse Event of Special interest associated with Jardiance®	immediately within 24 hours
All AEs with fatal outcome in patients exposed to Jardiance®, Trajenta® and/or Synjardy®	immediately within 24 hours
All non-serious Related Adverse Events associated with Jardiance®, Trajenta® and/or Synjardy®	7 calendar days
All pregnancy associated with Jardiance®, Trajenta® and/or Synjardy® on pregnancy monitoring forms	7 calendar days

The same timelines apply if follow-up information becomes available for the respective events. In specific occasions the Investigator could inform the Sponsor upfront via telephone. This does not replace the requirement to complete and secure email or fax the NIS AE form.

Reporting of DKA cases:

An additional information will be requested with a targeted form.

Information required

For each reportable adverse event, the investigator should provide the information requested on the appropriate e-CRF pages and the NIS AE form.

Reporting of related Adverse Events associated with any other BI drug

The investigator is encouraged to report all adverse events related to any BI drug other than **Jardiance®, Trajenta® and/or Synjardy®** according to the local regulatory requirements for spontaneous AE reporting at the investigator's discretion by using the locally established routes and AE report forms. The term AE includes drug exposure during pregnancy, and, regardless of whether an AE occurred or not, any abuse, off-label use, misuse, medication error, occupational exposure, lack of effect, and unexpected benefit.

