9.3.2 Exposures

The definition of drug exposure for Empagliflozin will be any patient using at least one prescription of Empagliflozin tablets (10 or 25 mg) or fixed-dose combinations with metformin. For the comparator group, the patients will have at least one prescription of DPP-4 inhibitors. DPP-4 inhibitor users included in this study will be using one of the following approved drugs in Saudi Arabia: Sitagliptin, Saxagliptin, Vildagliptin, Alogliptin, Linagliptin, or fixed-dose combinations of these drugs with metformin. [R17-3427]

Furthermore, each member of the population exposed to Empagliflozin must have at least one prescription for Empagliflozin, with or without other glucose-lowering drugs (GLDs), and have no prior prescriptions of a DPP-4 inhibitor or Empagliflozin during the available pre-index period. Each member of the population exposed to a DPP-4 inhibitor must have at least one prescription for a DPP-4 inhibitor, with or without other GLDs, and no prior prescriptions of a DPP-4 inhibitor or Empagliflozin during the available pre-index period.

Add-on therapy will be allowed after using the exposure of interest as the initial drug for new users. Therefore, using the drug as part of dual therapy or triple therapy will be allowed.

The use of studied medications will be defined on different levels: current use, recent use and discontinuation of the studied drugs. Current use of the index drugs will be defined from the date of prescription of Empagliflozin or DPP-4 inhibitor to the end of supply for that prescription plus a period of 30 days. Recent use will be defined from the end of current use (30 days after end of supply) until 90 days later (which is 120 days after end of supply).

Discontinuation of the index drug will be defined as no further prescription 120 or more days after the end of the last prescription's supply. Patients who discontinue an index drug and then subsequently initiate another index drug will not be allowed to re-enter the study.

Patients switching to or adding Empagliflozin to other antidiabetic medications will be compared to patients switching to or adding comparator treatment on the same background therapy. Identification of a "new-user" design is an appropriate method for studying second-line therapies in chronic conditions.

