4.7.5 Ketoacidosis, severe UTI, depletion and dehydration

As main endpoints, ketoacidosis, severe UTI (namely pyelonephritis and urosepsis), volume depletion and dehydration, will be derived from corresponding AE reporting. Crude and treatment-adjusted incidence rates will be presented by group and period, together with incidence rate ratios of EMPAGLIFLOZIN relative to DPP-4 inhibitor, as point estimates and with 95% confidence limits. Treatment-adjusted incidence rates are defined as crude incidence rates per 1,000 person-years. Per group, and, where appropriate, per stratum and/or subgroup, the number of person-years is the sum of length of index periods of all respective patients.

For each endpoint, the time from index date to first occurrence in days is determined. If the endpoint does not occur for a patient, the time is right-censored by the duration of the respective period, index period or follow-up period. By group, times to first occurrence will be described by means of Kaplan-Meier estimates with 95% confidence limits and, where appropriate, median times with 95% confidence limits.

Crude and treatment-adjusted incidence rates and respective incidence rate ratios will be described in summary tables by group and period, and per period in subgroups by metformin status, GLD status and insulin status, respectively. Ratios are defined as Empagliflozin to DPP-4 inhibitors.

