4.8 Handling of Missing Data

Data will be analyzed as reported. Missing data will not be replaced or imputed. Outlying values, if confirmed by site on data clarification, will be analyzed as reported.

Note that if specific endpoints (AEs i.e. ketoacidosis, volume depletion, dehydration serious UTI) are not reported for a patient in the AE section of the CRF it will be assumed that they did not experience that event.

Statistical Analysis Plan (SAP)

Document Date: 17APR2019

Document Version: 1.0 Final

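### Expedited reporting of ketoacidosis is product-specific and the scope of the targeted DKA form is not stated, so unequal capture of a primary outcome is a risk that the plan could cheaply remove

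*Protocol*

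**What the plan says.** Protocol 8.1 and SAP 2.1 make ketoacidosis one of four primary outcomes. Table 1 in Protocol 11.1 also lists it as an AE of special interest, without limiting it to a drug. The other three primary outcomes are not in that table.

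Table 2 in Protocol 11.2 sets out what must go on the NIS AE form and how fast. The special-interest row reads "Adverse Event of Special interest associated with Jardiance", with a limit of 24 hours. The serious-event row reads "All Serious Related Adverse Events (SAEs) with Jardiance® , Trajenta® and/or Synjardy". The rows for fatal events, non-serious related events and pregnancies name the same three brands. Under Protocol 9.3.2 the comparator cohort may take "Sitagliptin, Saxagliptin, Vildagliptin, Alogliptin, Linagliptin, or fixed-dose combinations of these drugs with metformin". Just below Table 2, under the reporting of DKA cases, the protocol says "An additional information will be requested with a targeted form". It does not state for which product or cohort.

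A separate, general rule in Protocol 11.2 covers the e-CRF: "The following must be collected by the investigator in the e-CRF from signing the informed consent onwards until the end of the study". The item that follows is all AEs, and all of them must be followed up, again without limit by drug. Protocol 9.3.1.1 and SAP 4.7.4 name both cohorts.

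SAP 4.7.5 says that the four outcomes "will be derived from corresponding AE reporting". SAP 4.8 adds that if an outcome is not reported in the AE section of the CRF, "it will be assumed that they did not experience that event".

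**The concern.** The comparison between cohorts is fair only if a ketoacidosis case has the same chance of being recognised, recorded and characterised in each. Table 2 singles out ketoacidosis on one product. A site that must send a 24-hour form for that product may become more alert to the event there.

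Little else in the plan would even this out:

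- The prescriber knows the treatment, and SAP 4.3 has no blinding.
- Visits 2 to 4 (Protocol 9.2.2.2 to 9.2.2.4) record AEs through an open item that names none of the four outcomes.
- The SAP visit schedule (Table 3-1) has blood glucose and other laboratory tests at Visit 1 only, and only if available.
- The documents describe no exposure-blind adjudication.
- Source data comparison covers about 10% of sites (Protocol 9.8).
- The propensity score balances baseline covariates. It cannot repair unequal outcome capture.

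Because silence is scored as no event, missed comparator cases would lower the comparator rate and raise the apparent IRR. Part of an observed excess on empagliflozin could then be an artefact of reporting.

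**Working it through.** The documents give no figure for capture, so there is nothing to reproduce. The check has three parts.

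**1. Two reporting channels side by side**

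| Feature | NIS AE form (Table 2) | e-CRF AE section |
|---|---|---|
| Events | Special-interest, serious related, fatal, non-serious related, pregnancy | All AEs |
| Products | Special-interest row: Jardiance only. Other rows: Jardiance, Trajenta, Synjardy | No limit |
| Follow-up of AEs | Same timelines for follow-up information on the listed events | Required for all AEs |
| Used for the outcome | Not stated | Yes (SAP 4.7.5 and 4.8) |

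The documents do not define Trajenta and Synjardy. I assume that they are linagliptin and the empagliflozin-metformin combination. Then four of the five DPP-4 inhibitors have no row in Table 2. Linagliptin patients have a 24-hour route for serious related ketoacidosis, and Synjardy patients in the empagliflozin cohort fall outside the special-interest row. The split is therefore by brand and only roughly by cohort.

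**2. Effect of unequal capture**

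Let c_E and c_D be the proportions of true cases recorded in the empagliflozin and DPP-4 cohorts, with no false positives. Then

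apparent IRR = true IRR × c_E / c_D.

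With true IRR = 1.00 and c_E = 0.95 (all capture values are assumptions):

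- c_D = 0.95: 0.95 / 0.95 = 1.00
- c_D = 0.90: 0.95 / 0.90 = 1.06
- c_D = 0.80: 0.95 / 0.80 = 1.19
- c_D = 0.70: 0.95 / 0.70 = 1.36

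The first line is what the e-CRF rule intends.

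**3. How few cases are involved**

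Protocol 9.5 plans 750 patients per group and Protocol 9 plans 12 months of follow-up. The most person-time per cohort, before any censoring, is therefore 750 person-years. Expected cases = rate × 750 / 1,000. The documents give no ketoacidosis rate, so the rates here are assumptions:

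| Rate per 1,000 person-years | Expected cases per cohort |
|---|---|
| 0.5 | 0.38 |
| 1 | 0.75 |
| 2 | 1.5 |
| 5 | 3.75 |
| 10 | 7.5 |

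Single cases matter at these counts. With three cases in each cohort and equal person-time the ratio is 3 / 3 = 1.0. If one comparator case goes unrecorded, it is 3 / 2 = 1.5.

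**The case against.** The strongest reply is that Table 2 governs the wrong channel. It sets a pharmacovigilance duty to forward reports to the sponsor, whereas the outcome is read from the e-CRF, where the rule is the same for both cohorts. A report form is filled in after the investigator has recognised an event, so nothing in the text shows that it increases detection. Protocol 9.3.4 also lists the diagnosis dates of the outcomes, ketones, pH and bicarbonate for all cohort members when available. Protocol 9.4 asks for hospital data on admissions for a study outcome, with no cohort limit.

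Most of this stands, and it rules out several stronger readings that a reader might infer:

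- That ketoacidosis is in fact pursued harder in one cohort. The documents show a product-specific duty, not its effect on e-CRF entries.
- That the targeted DKA form is limited to Jardiance. Its place directly below Table 2 invites that reading, but the sentence sets no limit.
- That all four primary outcomes are affected. Only ketoacidosis is on the special-interest list.
- That the IRRs above estimate the bias. They only restate assumed capture rates.

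The reply does not close the gap. An equal rule for entry does not ensure equal attention when treatment is known and the visit question is open. The variables in 9.3.4 are recorded only when available. Nothing states that a ketoacidosis case is to be characterised in the same way in both cohorts.

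**Conclusion.** The point holds as a risk of differential ascertainment for ketoacidosis, and not as a demonstrated bias. Its textual basis is firm: the special-interest row names Jardiance alone, most comparator drugs have no NIS AE form row (on the brand assumption above), the scope of the targeted form is unstated, and no report means no event.

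The likely direction, if capture is unequal, is towards a higher apparent IRR for empagliflozin. The size is not known. Under the assumed captures a true IRR of 1.00 would appear as anything from 1.00 to 1.36, and if e-CRF capture is equal there is no bias. These figures assume no false positives. Because few ketoacidosis cases can be expected, one or two missed cases could move the ratio materially.

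This is a cheap improvement to the plan. It does not invalidate the planned comparison.

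**What to change.** In Protocol 11.2, state that the targeted DKA form and one common e-CRF outcome page are completed to the same timeline for every ketoacidosis case in both cohorts, whatever the product. At Visits 2 to 4, replace the open AE item with questions that name the four primary outcomes, asked identically in both cohorts, and keep an open question for other AEs. Expedited forwarding to the sponsor's safety unit can stay product-specific.

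The cost is an existing form extended to comparator cases and four prompts on the visit pages. The extra site work is small because ketoacidosis cases should be few. Named questions may bring in a few more minor events, but in both cohorts.

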11.3 REPORTING TO HEALTH AUTHORITIES

Adverse event reporting to regulatory agencies will be done by the MAH according to local and international regulatory requirements.

